7.10 End of trial

The CLASP trial will proceed with an internal pilot phase, in which over the course of the initial 18 months we will recruit 36 sites (80% of total sites) and 246 participants (21% of total sample).

If the trial does not achieve 75% of these thresholds as defined below, it will be reviewed by the funding body with the anticipation of the trial being stopped:

- ≥ 27 sites
- ≥ 185 participants recruited
 - ≥ 0.54 Recruitment/Site/Month
 - ≥ 80% Participants with primary outcome

If these targets are achieved, the trial will end when the TSC agrees that one or more of the following situations applies:

- The planned sample size has been achieved
- The (IDMC) has advised discontinuation, e.g. because of safety concerns about the trial, or a statistically significant difference in clinical outcomes is evident between the two treatments
- There is insufficient funding to support further recruitment, and no reasonable prospect of additional support being obtained
- Recruitment is so poor that completion of the trial cannot reasonably be anticipated.

The trial sponsor will notify the MHRA of the end of the trial within 90 days of its completion. This will be when the last participant has completed the Day 90 follow-up visit. Should the trial terminate early, the sponsor will notify the MHRA within 15 days.

Prior to database lock, all data collection activities must have stopped, trial monitoring must have been completed, all primary and secondary outcomes must have been derived, and all data queries must have been resolved as far as is reasonably possible. At this point, the study blind will be broken for the trial statistical team, and the final analysis results will be produced.

8 TRIAL TREATMENTS

8.1 Name and description of investigational medicinal product(s) (IMPs)

The IMP in the CLASP trial is the macrolide antibiotic clarithromycin. Clarithromycin is a widely used macrolide antibiotic with well-known effect and side-effect profile. The current license includes use in lower respiratory tract infections such as acute and chronic bronchitis and pneumonia. In practice, use

includes empirical combination antibiotic treatment in aspiration pneumonia in true penicillin allergy and CAP.

Macrolides are a class of broad-spectrum antibiotics have both antimicrobial and immunomodulatory effects, and include clarithromycin, azithromycin and erythromycin. All macrolides share a common mechanism of antibacterial action which results in similar antimicrobial activity against Gram-positive bacteria such as *Staphylococci* and *Streptococci* and exhibit a degree of activity against certain Gram-negative organisms such as *Haemophilus spp*.[37]. Clarithromycin selectively binds to the 50s ribosomal sub-unit of susceptible bacteria preventing translocation of activated amino acids, inhibiting the intracellular protein synthesis of susceptible bacteria inhibiting growth.

8.2 Regulatory status of the drug

There are a number of different presentations available with a Marketing Authorisation within the UK. The following presentations are permitted for use in the study:

- Oral presentations such as tablets, granules for oral suspension and oral suspension
- IV presentations including concentrate for solution for infusion and powder for solution for infusion

Any brand of clarithromycin preparation listed above may be used provided they have a UK Marketing Authorisation.

Prolonged release oral clarithromycin tablets are not permitted for use in the CLASP study.

8.3 **Product characteristics**

For clinical information on clarithromycin, please refer to the relevant manufacturer's SmPC for the presentation(s) used at site.

8.4 Drug storage and supply

All supplies for use in the CLASP study will be sourced from routine NHS hospital stocks and will not be reimbursed. There is no requirement to 'ring-fence' supplies for use. Clarithromycin supplies should be stored in accordance with the applicable SmPC and relevant local policies on the storage of medicines. There is no requirement by Sponsor for sites to conduct temperature monitoring on IMP supplies but sites should follow their local SOPs.

8.5 Preparation, administration and labelling of Investigational Medicinal Product

Preparation and administration of clarithromycin should be performed in near-patient clinical areas in line with current practice requirements, the relevant SmPC and local practice such as IV monographs. All IMPs must be labelled in accordance with local requirements. There is no requirement for study specific labelling to be applied.

8.6 Dosage schedules

Participants randomised to the intervention arm will receive treatment with clarithromycin 500mg administered every 12 hours for 5 days (10 doses in total). A reduced dose of clarithromycin 250mg will be given in the event of renal impairment with eGFR <30 mL/min/1.73 m². See section 8.7 dose modification for further information. Clarithromycin treatment should commence as soon as possible after randomisation and be prescribed by an investigator (or designee) delegated this responsibility on the site delegation log in line with local requirements. It should be clear from the prescription that clarithromycin being administered as part of the CLASP study protocol.

Clarithromycin should preferably be administered via the intravenous or oral route as per the relevant SmPC. Where the enteral route is available, this should only be used if this route is considered by the

investigator to be the most appropriate route of administration. Enteral routes of administration for clarithromycin are unlicensed and may lead to variable absorption and are not generally recommended. Local guidance and requirements for administration of medicines via the enteral route as well as specific information for clarithromycin must be followed.

During the treatment period, investigators (or designees) must maintain regular oversight of clarithromycin dosing to ensure doses are administered as intended, the route of administration is appropriate and that treatment withdrawal criteria are not met. This should be evident from the participant's medical records. In the event a route of administration ceases to be available (e.g. loss of oral route due to dysphagia) or in the investigator's opinion is no longer appropriate or in-line with local policies such as IVOS, an alternate route may be considered. There is no limit to the number of times the administration route and/or presentation of clarithromycin may be changed. Changes to the presentation and route of administration must be clearly documented in the participant's usual care records.

The clinical condition of people with stroke often fluctuates during their admission. Whilst the investigator is required to maintain regular oversight, the participant's usual care team are permitted to amend clarithromycin dose and route of administration if necessary in order to meet the changing clinical needs of the participant and ensure ongoing safety. Supervision of people receiving antibiotics is a normal part of care in stroke units. Clinical staff are not required to undertake study-specific training nor are they required to be on the site delegation log as this is within the scope of their usual practice. A Clinical Information Sheet with key information including permitted dose modifications and stopping criteria is provided for insertion into the medical notes for patients randomised to the intervention arm.

In the event a participant is discharged to home or other off-site long-term care facility such as a nursing home, any remaining oral clarithromycin doses should be provided at discharge where appropriate. In the event the oral route is not available, clarithromycin must be stopped at discharge. Clarithromycin treatment must be discontinued in the event participants are transferred to another hospital or site that is not participating in the CLASP trial.

If doses are missed and ongoing treatment is not contraindicated, study drug can be continued so a total of 10 doses are given over a maximum period of seven days.

8.7 Dosage modifications

The following dose modifications will apply:

- At baseline or during treatment eGFR of <30 ml/min/1.73m²: Clarithromycin 250mg every 12 hours. Dose (re)escalation is permitted if eGFR improves within the treatment window.
- At investigator's discretion, the dose of clarithromycin may be reduced to 250 mg every 12 hours in the event of adverse effects.

Temporary stop to clarithromycin treatment

• Clarithromycin will be temporarily stopped if the participant is found to have hypokalaemia (defined as potassium <3.5 mmol/l) or hypomagnesemia (magnesium <0.70 mmol/l). At investigator's discretion, clarithromycin may be restarted once deficiency is corrected.

Criteria for permanent withdrawal of clarithromycin treatment are provided in section 7.9.1.

8.8 Known drug reactions and interaction with other therapies

Clarithromycin is a widely used macrolide antibiotic, with a known potent inhibitory effect on CYP34A. Drugs that are primarily metabolised by CYP34A may have elevated and prolonged therapeutic concentrations when administered concomitantly with clarithromycin and are prohibited. Conversely, drugs which are potent inducers of CYP3A may lower the plasma levels of clarithromycin and are

therefore also prohibited. The most likely relevant drug interactions in this population are use of statins and ticagrelor. However, a participant may still be enrolled if, in the local investigator's opinion and judgement, the prohibited medication can be temporarily stopped during the duration of the clarithromycin treatment (see section 8.9 below).

For detailed information on drug-drug interactions, please refer to the relevant SmPC or other local prescribing resources. Prohibited concomitant medicines are provided in Appendix 2. Please note this list is not exhaustive. Medicines with a known interaction which may be co-administered at investigator's discretion are provided in Appendix 3. See also information on permitted dose modifications in section 8.7.

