The potential risks associated with clarithromycin will be minimised by avoiding use in people who are known to be intolerant (included as a trial exclusion criteria) and avoiding concomitant use with medicines which have known interactions or increase risk of QT prolongation. Concomitant use of medicines that are listed as contraindicated in the SmPC or as 'manufacturer advises avoid' in the BNF will not be permitted unless these can safely be stopped or temporarily withheld for the duration of clarithromycin treatment plus 3 days (72 hours) to allow >5 half-lives to elapse. In addition, we have excluded additional medications which could be associated with adverse reactions that could be difficult to detect or where clarithromycin levels could be significantly reduced. These are listed in Appendix 2. In addition, medications that can interact with clarithromycin but can be used with caution are listed in Appendix 3. The use of anticoagulant drugs is allowed after consideration of the risks and benefits. There is emerging evidence that DOACs pose little risk of bleeding complications in the early period after ischemic stroke and would not normally be use in people with intracerebral haemorrhage. Stroke physicians are well experienced in assessing these relative risks and benefits. The use of

calcium channel blockers, digoxin and drugs for diabetes mellitus is allowed as these can be readily monitored in routine practice and stroke physicians are experienced with these drugs. Corticosteroids, cilostazol and omeprazole use is allowed as the potential for significant adverse effects is low with a short duration of treatment. Omeprazole and cilostazol can usually be withheld for a short period or alternative agents can be used.

In addition, risk is mitigated by the fact participants will be randomised and initially treated in acute stroke services and by avoiding clarithromycin use in the following people:

- People with QT prolongation
- People with a history of long QT syndrome or ventricular arrhythmia or cardiac arrest.

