People with these features will also be excluded from the trial. Hypokalaemia and hypomagnaesemia are also risk factors for QT prolongation. People with known hypokalaemia (defined as K+ < 3.5 mmol/l) or known hypomagnaesemia (defined as Mg2+ < 0.70 mmol/l) at the point of screening will be excluded from the trial. They can later be included if this is corrected and they remain eligible. People with hypokalaemia or hypomagnesaemia prior to screening that has already been corrected can also be included.

Clarithromycin is routinely used in clinical practice and information on clinically relevant interactions and contra-indications is well documented and easily accessible (e.g. SmPC and BNF), further minimising potential risks.

Clostridioides difficile infection is a documented risk from use of antibiotic therapy. There is uncertainty regarding any excess risk from clarithromycin use. An evidence summary published by NICE in 2015 [23] found that macrolides are likely to be associated with an increased risk of *C.difficile* infection but this risk is equivalent to use of penicillins and is likely less than antibiotics such as clindamycin, cephalosporins and tetracyclines [24].

Statins will be frequently used in this population. People prescribed statins can be randomised but suspension of statin therapy whilst receiving clarithromycin is required by the protocol [25]. There is no RCT evidence to support use of statins earlier than 7 days after stroke onset [26] and no evidence that delaying statin use for a short period will be detrimental.

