6.2 Exclusion criteria

- Requirement for macrolide therapy as usual care
- Confirmed respiratory viral infection (e.g. COVID-19, influenza) at point of screening*
- Known antibiotic treatment for chest infection or pneumonia within the last two weeks (single doses or less than 3 days of treatment is allowed)
- Known toxin positive *C.difficile* infection in the past 12 weeks
- Contraindications or major cautions to macrolide antibiotic use:
 - Known hypersensitivity to clarithromycin, its excipients or other macrolide antibiotics
 - Established diagnosis of myasthenia gravis
 - Diagnosis of long QT syndrome
 - QTc interval >460ms on last ECG before screening[†][36]
 - Known hypokalaemia (K+ < 3.5 mmol/l) which has not been corrected

- Known hypomagnesaemia (Mg2+ < 0.70 mmol/l) which has not been corrected
- History of ventricular tachycardia
- History of cardiac arrest
- Severe hepatic impairment defined as AST, ALT or bilirubin > 3 times ULN or known diagnosis of cirrhosis
- Current use of medicine(s) known to increase risk of QT prolongation that in the opinion of the investigator cannot reasonably be withheld for the duration of study treatment plus 3 days (see Appendix 2)
- Current use of medicine(s) that are contra-indicated in combination with clarithromycin that in the opinion of the investigator cannot reasonably be withheld for the duration of study treatment plus 3 days (see Appendix 2)
- Women of childbearing potential who are pregnant, breastfeeding or who are unwilling to use appropriate contraception or abstain from sexual intercourse for 3 days (72 hours) after the last dose of clarithromycin (see Appendix 1 for definitions and information on acceptable methods of contraception)
- Plan for imminent mechanical ventilation
- End-of-life care
- Previously randomised into the CLASP study

* A test for viral infection is not required by protocol, this is only if it is done for routine clinical care.

[†]Some ECG machines may provide different measures of QTc. For trial eligibility, the longer result should be used.

Co-enrolment in other Clinical Trial of Investigational Medicinal Products (CTIMPs) is not permitted while participating in CLASP. Co-enrolment in observational studies, diagnostic studies or other research may be permitted subject to agreement of the Sponsors and Chief Investigators of both studies.

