7.9 Withdrawal criteria

7.9.1 Withdrawal from clarithromycin treatment (intervention arm)

Participants may be withdrawn from the study treatment by local clinical teams in the event of a Serious Adverse Reaction (SAR) and it is felt that it is in the best interest of the patient to discontinue treatment. Participants allocated to the intervention arm will also be withdrawn from clarithromycin treatment in the event:

- Treatment is initiated with a prohibited medicine, where the prohibited medicine has not been temporarily discontinued by the local PI (see Appendix 2)
- Requirement for macrolide therapy as part of evolving antibiotic use
- Known toxin positive *C.difficile* infection
- The participant deteriorates after enrolment and becomes for palliative care only
- Onset of contraindications or major cautions to macrolide antibiotic use:
 - Hypersensitivity to clarithromycin, its excipients or other macrolide antibiotics
 - Diagnosis of long QT syndrome
 - Any event of QTc prolongation of >20ms compared to the baseline value
 - Ventricular tachycardia
 - Cardiac arrest
 - Any occurrence of severe hepatic impairment defined as AST, ALT or bilirubin >3 times ULN

Discontinuation of treatment by local clinical teams does not require withdrawal of the participant from the study and follow-up can be continued.

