8.9 Concomitant medication

A participant's concomitant medication should be checked by a medically qualified investigator before randomisation to ensure eligibility and to ensure appropriate action is taken regarding concomitant medication.

Participants prescribed or taking prohibited medicines as listed in Appendix 2 are ineligible for the study unless in the investigator's opinion the interacting medicine can safely and appropriately be withheld for the duration of clarithromycin treatment plus 3 days. Should an indication for these drugs develop during the study treatment period and treatment with a prohibited medicine commence, participants must be withdrawn from study clarithromycin treatment. Participants will also permanently stop trial clarithromycin treatment should clarithromycin (or other macrolide) become clinically indicated for antibiotic treatment as per local antimicrobial policies. Relevant data should continue to be collected on participants providing consent is still in place.

Participants prescribed or taking medication listed in Appendix 3 can be enrolled in the study at investigator discretion following consideration of advice contained in the protocol, the BNF and the SmPC.

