Appendix 2: Prohibited concomitant medicines

This list is not exhaustive but is based on drugs listed as contraindicated in the SmPC, as 'manufacture advises avoid' in the BNF, and additional drugs identified by the Sponsor to maximise safety. Please refer to the relevant Summary of Product Characteristics or contact the Sponsors for further advice.

| Prohibited Medicines |
|--|
| Abemacicib |
| Alprazolam |
| Amiodarone |
| Anti-arrhythmic drugs (e.g. Quinidine) Astemizole, |
| Atypical antipsychotics (e.g. quetiapine) Avanafil |
| Avapritinib |
| Axitinib |
| Bedaquiline |
| Cabergoline |
| Carbamazepine |
| Cariprazine |
| Ciclosporin |
| Chloroquine |
| Cisapride |
| Colchicine |
| Crizotinib |
| Daridorexant |
| Darifenacin |
| Disopyramide |
| Domperidone |
| Dronedarone |
| Eletriptan |
| Ergometrine |
| Ergot alkaloids – ergotamine and dihydroergotamine |

| Prohibited Medicines |
|---|
| (cont) Everolimus |
| Fidaxomicin |
| Fineronone |
| Grazoprevir |
| HIV infection drugs. e.g. efavirenz, nevirapine, saquinavir, ritonavir, atazanavir, zidovudine Hydroxychloroquine |
| Ibrutinib |
| Irinotecan |
| Itraconozole |
| Ivabradine |
| Lapatinib |
| Lercanidipine |
| Lomitapide |
| Lurasidone |
| Methadone |
| Midazolam |
| Mizolastine |
| Mobocertinib |
| Naloxegol |
| Nilotinib |
| Phenytoin |
| Pimozide |
| Pimozide |
| Quetiapine |
| Ranolazine |

| Prohibited Medicines (cont) |
|--|
| Reboxetine |
| Rifabutin |
| Rifampicin |
| Rifapentine |
| Rimegepant |
| Rupatadine |
| Salmeterol |
| Phosphodiesterase 5 inhibitors e.g. sildenafil, tadalafil, vardenafil. This applies to concurrent use only. Sirolimus |
| Statins / HMG CoA enzyme reductase inhibitors. |
| For purposes of this study, all statins are contraindicated Tacrolimus |
| Temsirolimus |
| Tepotinib |
| Terfenadine |
| Theophylline |
| Ticagrelor |
| Tolterodine |
| Valproate |
| Vardenafil |
| Verapamil |
| Vinblastine |
| Voclosporin |

Appendix 3: Medicines with known interactions with clarithromycin but may be used with caution at investigator's discretion

| Medicines where there may be drug interactions and caution is advised | Comments | | |
|---|---|--|--|
| Direct acting oral anticoagulants e.g. dabigatran, rivaroxaban, apixaban and edoxaban | Use concurrently with caution and consider individual risk of bleeding. | | |

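### Sections 7.9.1 and 8.9 give opposite stop rules when a prohibited medicine is started and then paused; a lesser inconsistency leaves 3 days out of the withholding period in two places

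*Protocol*

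**What the plan says.** **Starting a prohibited medicine during treatment.** Section 8.9 deals with an indication for such a medicine arising in the study treatment period. It says that, should "treatment with a prohibited medicine commence, participants must be withdrawn from study clarithromycin treatment". Section 7.9.1 lists the events that lead to withdrawal from clarithromycin, and its first item reads: "Treatment is initiated with a prohibited medicine, where the prohibited medicine has not been temporarily discontinued by the local PI". Section 8.7 refers the reader to 7.9.1 for the criteria for permanent withdrawal.

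**Withholding a medicine.** Three places give treatment plus 3 days:

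- Section 2.1.1, general rule: "temporarily withheld for the duration of clarithromycin treatment plus 3 days (72 hours) to allow >5 half-lives to elapse".
- Section 6.2, in two exclusion criteria: excluded if the medicine "cannot reasonably be withheld for the duration of study treatment plus 3 days (see Appendix 2").
- Section 8.9: ineligible unless the medicine can "safely and appropriately be withheld for the duration of clarithromycin treatment plus 3 days".

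Two places mention the time on clarithromycin without the 3 days:

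- Section 8.8, as a condition for enrolment: "the prohibited medication can be temporarily stopped during the duration of the clarithromycin treatment (see section 8.9 below").
- Section 2.1.1, on statins: "suspension of statin therapy whilst receiving clarithromycin is required by the protocol".

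Appendix 2 puts statins on the prohibited list: "For purposes of this study, all statins are contraindicated".

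**The concern.** These are safety rules that ward and research staff must apply within a few days. Section 8.8 names statins and ticagrelor as the most likely relevant interactions, and section 2.1.1 expects statin use to be common in this population and describes the muscle toxicity at issue.

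If two sections answer the same question differently, the decision to stop or continue clarithromycin depends on which one was read. Section 8.6 adds to this: the usual care team may adjust clarithromycin without study-specific training, and a Clinical Information Sheet with stopping criteria goes into the notes of participants in the intervention arm. That sheet is not among the documents, but it has to be drawn from a protocol that states the stop rule in two forms.

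A site that follows one section may also be recorded as deviating from another, and section 13.5 treats frequently recurring deviations as a possible serious breach.

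**Working it through.** There is no stated figure to reproduce. The check is a comparison of the sections, plus arithmetic on the stated durations.

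**1. Stop rule.** Take a participant on clarithromycin who is started on an Appendix 2 medicine.

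| What happens next | Section 7.9.1 | Section 8.9 |
|---|---|---|
| The new medicine continues | withdraw from clarithromycin | withdraw from clarithromycin |
| The local investigator pauses the new medicine | withdrawal criterion not met | withdraw from clarithromycin |

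The sections agree in the first row and conflict in the second. Section 8.9 has no exception and does not point to 7.9.1. The item in 7.9.1 points to Appendix 2, not to 8.9. The reference in 8.7 leads to the conditional version. Section 2.1.4 lets clarithromycin continue when antibiotics are added, provided that they are not on the Appendix 2 list. It says nothing of a listed medicine that is started and then paused, so it does not settle the second row.

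**2. Withholding period.** Inputs:

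- Planned course: 5 days, 10 doses (section 8.6).
- Longest permitted course when doses are missed: 7 days (section 8.6).
- Added interval: 3 days, that is 3 × 24 = 72 h (sections 2.1.1, 6.2 and 8.9).

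| Course | Sections 8.8 and 2.1.1 (statins) | Sections 2.1.1 (general), 6.2 and 8.9 | Difference |
|---|---|---|---|
| Planned | 5 days | 5 + 3 = 8 days | 3 days = 72 h |
| Longest permitted | 7 days | 7 + 3 = 10 days | 3 days = 72 h |

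The difference does not depend on how the end of treatment is counted. If an uninterrupted course is timed to its last dose, that dose falls at 9 × 12 = 108 h, or 4.5 days, and the two endpoints are 4.5 and 4.5 + 3 = 7.5 days. The gap is again 72 h, which is the whole of the added interval.

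**3. Can a reader resolve it from the protocol?** For section 8.8, largely yes: it sends the reader to 8.9, and both exclusion criteria in 6.2 carry the 3 days. The statin sentence has no such reference. A reader has to notice that Appendix 2 lists all statins and infer that the general rule applies to them. For the stop rule there is no text that decides between 7.9.1 and 8.9.

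**The case against.** The best defence concerns the withholding period. Section 8.8 states a condition for enrolment, is silent on restarting, and is followed directly by 8.9, to which it refers. The statin sentence is rationale, placed in the same section that has already set the longer period. Neither says that suspension may end with the last dose. The exclusion criteria say plus 3 days twice, and section 13.5 forbids enrolling anyone who does not meet eligibility. This largely stands. It makes the second point incomplete wording in subordinate text, not two rules of equal rank.

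On the stop rule, it can be said that the conflict is narrow: it needs a prohibited medicine to be started within a course of 5 to 7 days and then paused. That is true, and the protocol gives no frequency. It could also be argued that the exception in 7.9.1 was meant for medicines already paused at enrolment. The item speaks of treatment being initiated, however, so its wording does not confine it to those.

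A reader might infer more than the text supports:

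- **That 72 h must pass before any newly needed prohibited medicine is given, so that both stop rules break the protocol's own margin.** The 72 h interval is stated for withholding medicines already prescribed or taken. No section applies it to new starts, so there is no contradiction on that point.
- **That every statin user in the clarithromycin arm is affected.** At most it concerns those whose medicine is restarted within 72 h of the last dose.
- **That the 72 h interval is the main safeguard.** Section 2.1.1 lists several, among them exclusions for QT prolongation and electrolyte disturbance, and monitoring in acute stroke services.

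**Conclusion.** Both inconsistencies are in the current text. The stop rule is the main one: for a prohibited medicine started during treatment and then paused, 7.9.1 and 8.9 lead to opposite actions, and nothing in the protocol ranks one above the other. The withholding period is the lesser one: two places leave out 72 h that three others include, but a site reading 6.2 and 8.9 together arrives at 8 days for the planned course, or 10 for the longest.

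How many participants either point touches cannot be estimated. The protocol gives neither the share on statins nor the frequency of new prohibited prescriptions. The finding does not depend on the half-life argument in 2.1.1, which cannot be checked because no half-life is given. The consequences are for participant safety and consistent conduct across sites. Sample size, power and alpha are unaffected. No view is taken here on which stop rule or which period is right.

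**What to change.** The sponsor should:

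1. Reconcile sections 7.9.1 and 8.9 so that both state the same stop rule, including what applies when the new medicine is paused.
2. Reconcile section 8.8 and the statin sentence in 2.1.1 with the general rule in 2.1.1, section 6.2 and section 8.9, so that one withholding period appears throughout.
3. Check that the Clinical Information Sheet carries the same stop rule and the same period.

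The sponsor decides the content of both rules. The cost is a wording amendment to a few sentences, and a revision of the sheet if it differs. Visits, sample size and analysis do not change.
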